### **7.3.3 Visit #4 (Day 11 + 3 days)**

Study subjects will be evaluated on Day 11 via telephone. Secondary and exploratory outcome measures will be assessed at this follow up. Study staff will complete the following procedures:

- Assessment of clinical improvement including:
  - Review and collection of temperature
  - Assessment and grading of LRTI symptoms
  - Occurrence of any medically attended visits
  - Receipt of any non-study systemic antibiotics
- Review of the subject's memory aid
- Assess and record any solicited events and UADEs

If the subject develops signs or symptoms of pneumonia (including fever, increased work of breathing, or increased/worsening cough) or develops a severe solicited event, the subject will be referred to his/her primary care provider or local urgent care center/ED. Study staff will assist in facilitating the follow up appointment. The study staff will share all pertinent information related to the study with the treating clinician including treatment arm assignment if clinically indicated as determined by the treating clinician and the study's site investigator.

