## **5.4 Treatment Assignment Procedures**

### **5.4.1 Randomization Procedures**

Per International Council on Harmonisation (ICH) guideline E6: Good Clinical Practice (GCP), screening records will be kept at each participating site to document the reason why an individual was screened, but failed trial entry criteria. The reasons why individuals failed screening will be recorded on screening logs maintained by each site. Once consented and upon entry of demographic data and confirmation of eligibility for this trial, the subject will be enrolled. Only if the PCT is confirmed to be  $\leq 0.25$  ng/mL, will the subject be randomly assigned to 1 of 2 groups (1:1 ratio) to receive either azithromycin or placebo. Subjects with a PCT  $> 0.25$  ng/mL will remain enrolled but will not be randomized to receive study drug.

Enrollment of subjects will be performed online using AdvantageEDC. Lists of randomized treatment assignments will be prepared by statisticians at The Emmes Corporation and included

in The Emmes Corporation's Internet Data Entry System (IDES). IDES will assign each randomized subject a treatment code from the list after the necessary data has been entered into the system. Each site will have a supply of bottles pre-labeled with treatment numbers. Once a participant is assigned a treatment number, the corresponding bottle will be distributed to the participant. An unblinded pharmacist at each site will be provided with a treatment key, which links the treatment code to the actual treatment assignment, which will be kept in a secure place. Subjects will be stratified by site.

Instructions for subject enrollment are included in the Manual of Procedures (MOP). Manual back-up randomization procedures are provided in the MOP for use in the event that the site temporarily loses access to the Internet or the online enrollment system is unavailable.

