### **5.4.2 Masking Procedures**

This is a double-blind clinical trial with respect to treatment arm. Subjects, investigators, study personnel performing any study-related assessments following randomization, and laboratory personnel performing assays will be blinded to treatment group assignment.

The study product and placebo will be dispensed by the site Research Pharmacist. The study product will be labeled with a numerical code that ensures site investigators, site staff, and subjects remain blinded to the treatment assignment. For subjects randomized to placebo, the placebo will resemble the appearance of the active study product. All study products will be packaged with an identical appearance. The site Research Pharmacist will be blinded to the treatment assignment at the time product is dispensed but may be unblinded to an individual subject's treatment assignment, if clinically indicated as determined by the treating clinician and the study's site investigator.

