## **6.4 Accountability Procedures for the Study Intervention/Investigational Product(s)**

### **6.4.1 Azithromycin and Placebo**

After receipt of the study product, the site Principal Investigator (PI) is responsible for distribution and disposition of these study products, and has ultimate responsibility for drug accountability. As this is a blinded study, the site PI will delegate this responsibility to the unblinded site pharmacist. Study product records must be maintained and document logs of receipt, accountability, and storage temperature conditions. These study product accountability and dispensing logs must be maintained in the study file. Upon completion of the study and after the final monitoring visit, unused study product that has not been dispensed will be retained until monitored and released for disposition as per the Sponsor.

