### **7.3.2 Visit 3 (Day 5 + 3 days)**

The visit on Day 5 will represent the primary outcome assessment and will include an assessment of LRTI signs and symptoms. Also at Day 5, blood samples will be collected for repeat PCT testing. To permit evaluation of the secondary RADAR outcomes, all clinical parameters pertinent to the RADAR assessment will be ascertained at this time. This will be an in-person visit conducted at the study site. This visit can also be conducted in the subject's home.

Prior to this visit, study staff will make a preliminary assessment of the clinical response using the electronic health record to determine whether any of the following events have occurred after randomization and anticipated receipt of at least one dose of study agent.

- The subject had a medically attended visit to an ED, urgent care, or clinic;
- The subject was hospitalized during a separate clinical encounter following the enrollment encounter
- The subject received non-study, systemic antibiotic therapy

At the Day 5 visit, study staff will complete the following procedures:

- Assessment of clinical improvement including:
  - Review and collection of vital signs
  - Assessment and grading of LRTI symptoms
  - Occurrence of any medically attended visits
  - Receipt of any non-study systemic antibiotics
- Abbreviated physical examination to include general appearance and focused HEENT, neck, cardiopulmonary, and abdominal examinations;
- Review of the subject's memory aid
- Assess and record any solicited events and UADEs
- Review of memory aid and study product bottle (if available) to assess treatment compliance
- Obtain blood sample for PCT testing
- Review of study product bottle for drug accountability, if available;

If the subject develops signs or symptoms of pneumonia (including fever, increased work of breathing, increased/worsening cough, or new pulse oximetry reading  $\leq 90\%$ ) or develops a severe solicited event, the subject will be referred to his/her primary care provider or local urgent care center/ED. Study staff will assist in facilitating the follow up appointment. The study

staff will share all pertinent information related to the study with the treating clinician including treatment arm assignment if clinically indicated as determined by the treating clinician and the study's site investigator.

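### Protocol 7.3.2–7.3.4 have study staff, the same term used for those who grade symptoms, relay the treatment arm, in conflict with 5.4.2; a later grade, mainly at Day 28, may then be made unblinded

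*Protocol*

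**What the plan says.** Protocol 5.4.2 sets the masking rule: "Subjects, investigators, study personnel performing any study-related assessments following randomization, and laboratory personnel performing assays will be blinded to treatment group assignment". It then turns to the site Research Pharmacist, who is said to be blinded when handing out product, with one exception: this person "may be unblinded to an individual subject's treatment assignment, if clinically indicated as determined by the treating clinician and the study's site investigator". No one else is named as open to individual unblinding.

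The visit sections use a different actor. In 7.3.3 (Visit 4), a subject with signs of pneumonia or a severe solicited event is referred for care, and the text then says: "The study staff will share all pertinent information related to the study with the treating clinician including treatment arm assignment if clinically indicated". Sections 7.3.2 (Visit 3) and 7.3.4 (Visit 5) carry the same clause. In all three it has the same qualifier as 5.4.2: the treating clinician and the site investigator decide. All three sections also assign the visit procedures, including grading of LRTI symptoms, to study staff. The term is not defined.

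Section 9.5.2 allows unblinding on request under the same condition. It sets no visit limit and does not say who obtains or passes on the assignment.

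The pharmacist's status is described in two ways. Section 5.4.1 says "An unblinded pharmacist at each site will be provided with a treatment key", and 6.4.1 says "the site PI will delegate this responsibility to the unblinded site pharmacist". Section 5.4.2 says "The site Research Pharmacist will be blinded to the treatment assignment at the time product is dispensed". SAP 4.4.3 and 4.4.4 carry the same two descriptions.

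**The concern.** Clinical improvement at every time point turns on one-step changes in symptom severity, in a placebo-controlled non-inferiority trial. Grades of that kind are open to influence if the person recording them knows the arm. Unblinding under these clauses would be concentrated in subjects who are doing badly or have a severe solicited event, and their numbers may differ between arms. If the person who relays the arm later grades the same subject, the Day 28 comparison, and to a lesser extent the Day 11 comparison, loses some of the protection that 5.4.2 promises. The inconsistency sits in the visit instructions that sites follow day to day.

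**Working it through.** The plan states no unblinding rate, so there is no figure to reproduce. The check sets the sections side by side.

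**1. Who may know the arm**

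| Section | Who | Status |
|---|---|---|
| 5.4.1, 6.4.1 | Site pharmacist | Unblinded; holds the key (5.4.1) and accountability (6.4.1) |
| 5.4.2 | Research Pharmacist | Blinded at dispensing; may be unblinded for one subject |
| 5.4.2 | Investigators and post-randomization assessors | Blinded |
| 7.3.2–7.3.4 | Study staff | Pass the arm to the treating clinician if clinically indicated |
| 9.5.2 | No one named | Unblinding on request, same condition |

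The condition for unblinding agrees throughout. The person who handles the assignment does not. Nothing supplied says that the relay must be a non-assessor, or that a still-blinded person must make later gradings.

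**2. Which grades the 7.3 clause can reach**

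- Visit 3: the grading procedures come first; referral and sharing follow. The Day 5 grade is already made. Day 11 and Day 28 lie ahead.
- Visit 4: only Day 28 lies ahead.
- Visit 5: it is the last visit, so no later grade is affected.
- Before Visit 3: the Day 3 call (7.3.1) includes referral but no sharing of the arm. Unblinding before Day 5 could arise only through 9.5.2 or the exception in 5.4.2.

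**3. How far staff shape the later grades**

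- Day 11: SAP 6.5.2 takes severity from the daily form for study day 11. Subjects keep a memory aid through Visit 4 (Protocol 8.1), which coordinators review for gaps and discrepancies and then record. Staff influence is reduced but not removed.
- Day 28: SAP 6.5.2 takes severity from the symptom form at Visit 5, a telephone visit conducted by study staff. The memory aid has ended by then, so no diary stands behind this grade.

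**4. Who is exposed**

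Under Protocol 3.2.2 (items 6 and 7), a medically attended visit or hospitalization for LRTI with a non-study antibiotic, at any time after randomization, makes the subject a failure at Day 11 and Day 28. No symptom grade can change that. What remains is a subject who is referred, has the arm shared, and receives no such antibiotic, for example one referred for a severe solicited event.

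**5. What is recorded**

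The SAP Table 5 shell has a deviation row for unblinded treatment, and Listing 3 gives the study day of each deviation. Unblinding that 7.3 or 9.5.2 permits is arguably not a deviation, so it might not be logged. Nothing asks whether it came before a given grading.

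**The case against.** The strongest reply is that this is loose drafting. Sharing is conditional and per subject, and 5.4.2 carries the same condition, so individual unblinding is consistent with the masking plan. Study staff could mean the pharmacist or someone who does not grade. The Manual of Procedures, which is not supplied, may already separate the roles. Grades have written anchors, telephone answers come from the subject, and many referred subjects will be fixed as failures by the antibiotic criterion. SAP 8.1.1 rests the non-inferiority conclusion on the Day 5 primary analysis alone. A grader who expects the antibiotic to help would mark placebo down, which makes non-inferiority harder to conclude, not easier. The pharmacist is not described as grading anything, so that inconsistency alone creates no endpoint bias.

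Most of this stands, and it limits the point to a route to unblinded grading that the text leaves open. It does not remove the conflict: the visit sections give grading and relaying to the same undefined group, while 5.4.2 keeps assessors blinded.

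A reader might infer more: that outcome gradings are in fact made by unblinded assessors, or that the primary Day 5 result is compromised by the visit clauses. The documents support neither. No section says that assessors are told the arm or that it is shared routinely. The Visit 3 clause follows the Day 5 grading, and nothing is graded after Visit 5.

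**Conclusion.** The point holds in limited form. Protocol 7.3.2–7.3.4 and 5.4.2 conflict on who learns and relays the arm, and 5.4.1 and 6.4.1 conflict with 5.4.2 on whether the site pharmacist is blinded. As written, a grader may learn a subject's arm at Visit 3 or 4 and then grade that subject, with Day 28 the clearest exposure.

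No numerical size is given, because neither the unblinding rate nor the share of grades that would change can be drawn from the documents. The exposed group is small. The expected effect is small and falls mainly on secondary comparisons: the Day 28 non-inferiority analyses (ITT and ATP-28) and, less so, those at Day 11. The conclusion assumes that no separation of roles exists outside the supplied documents. It merits correction because the change protects assessor blinding at almost no cost.

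**What to change.** - Reword 7.3.2–7.3.4 and 9.5.2 so that, once unblinding has been judged clinically indicated, the key-holding pharmacist gives the assignment directly to the treating clinician. Staff who will grade later visits are not told. The joint decision by clinician and site investigator does not require site staff to know the arm.
- If a grader learns the arm anyway, have a still-blinded member of the existing team make that subject's remaining assessments.
- Record the date of every unblinding, including permitted ones, so that it can be placed before or after each grading.
- Reconcile 5.4.1, 5.4.2 and 6.4.1, and SAP 4.4.3 and 4.4.4, on which pharmacist holds the key and whether the dispensing pharmacist is the same person.

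When unblinding is indicated stays as it is. The cost is protocol wording and one date field. The practical change is that the treating clinician deals with the pharmacist instead of study staff.

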### **7.3.4 Visit # 5 Final Visit (Day 28 ± 2 days)**

Study subjects will be evaluated on Day 28 via telephone. Secondary outcome measures will be assessed at this follow up. Study staff will complete the following procedures:

- Assessment of clinical improvement including:
  - Review and collection of temperature
  - Assessment and grading of LRTI symptoms
  - Occurrence of any medically attended visits
  - Receipt of any non-study systemic antibiotics
- Assess and record any UADEs

If the subject develops signs or symptoms of pneumonia (including fever, increased work of breathing, or increased/worsening cough) or develops a severe solicited event, the subject will be referred to his/her primary care provider or local urgent care center/ED. Study staff will assist in facilitating the follow up appointment. The study staff will share all pertinent information

related to the study with the treating clinician including treatment arm assignment if clinically indicated as determined by the treating clinician and the study's site investigator.

The study staff will also review any new or changed con-commitment medications with the subject. A review of the medical record will also be done to recording results of clinical laboratory evaluations as specified in Section 8.2.1.

The exact date of the follow-up visit will be documented throughout the study.

### **7.3.5 Early Termination Visit**

Subjects who are withdrawn from the study will be asked to complete an early termination visit. Procedures at the early termination visit will be identical to the next scheduled visit for outcome assessment. Subjects who withdraw from the study will be asked if they agree to receive a follow-up phone call approximately one week after their withdrawal, which will constitute the early termination visit. If the subject agrees, study staff will determine if any follow-up medical care was sought, any solicited adverse events occurred or if there was any change in medical history.

If the subject presents to the Early Termination visit with symptoms concerning for active illness in need of medical attention, such as fever and/or elevated respiratory rate, the study team will refer the subject to seek care and to follow up with their primary care provider.

UADEs will be recorded if any occur.

### **7.3.6 Unscheduled Visit**

N/A

## **7.4 Follow-up for Non-randomized Subjects**

### **7.4.1 Visit #5N (Day 28+7)**

At enrollment, subjects with a PCT level > 0.25 ng/ml will still have data and samples collected but they will not be randomized. Their charts will be reviewed through 28 days after enrollment in order to support future use research. This may include recording the results of clinical laboratory evaluations as specified in Section 8.2.1. Review of medical history will be performed to determine whether medically attended visits or receipt of systemic antibiotics have occurred.

## 8 STUDY PROCEDURES/EVALUATIONS

### 8.1 Clinical Evaluations

A medical history will be obtained by direct interview during the screening process. Potential subjects will be queried regarding a history of significant comorbidities, current medications, and allergies including drug allergies. Medication history (concomitant medications) will include a review of all medications taken in the last 30 days (see section 6.6. for details). Use of non-study systemic antibiotics will be reviewed at each visit following enrollment. Concomitant medications will be reported in the eCRF. Prescription and over-the-counter drugs will be included as well as herbals, vitamins and supplements. Use of new medication should prompt evaluation for the presence of a new diagnosis of an acute or chronic medical disease or condition. At follow-up visits, an interim medical history will be obtained by interview of subjects noting any changes since the previous clinic visit or contact. The interim medical history should include an assessment for new medical conditions.

At the enrollment visit (Day 1), a clinical assessment to assess eligibility will occur, which will include vital signs (temperature, blood pressure, pulse, respiratory rate, and pulse oximetry). If indicated based on subject's medical history or medical/nursing assessment, a physical examination, conducted as part of the clinical care or by a study clinician licensed to make medical diagnoses\*, will occur. This could include a focused HEENT, neck, cardiopulmonary, and abdominal examinations.

An assessment of clinical improvement will occur at each follow-up visit. The assessment will include documentation of maximum temperature in the preceding 24 hours; normalization of respiratory rate (at the in-person visit); presence and extent of cough, sputum production, chest pain, and difficulty breathing; occurrence of medically attended visits including visits to the emergency department (ED), primary care physician, study physician, and urgent care; hospitalizations; and use of non-study systemic antibiotics (parenteral or oral). Vital signs (temperature, blood pressure, pulse, pulse oximetry, and respiratory rates) will be collected at the enrollment visit and at each in-person follow-up visit.

Solicited event assessments will include an assessment of solicited events occurring from the time of enrollment through Visit 4 (Day 11+3 days). All subjects will be instructed to complete a subject memory aid from the time of enrollment through Visit 4 (Day 11+3 days). Subject memory aids will be reviewed with the subject for any discrepancies or missing data and data will be recorded by study coordinators.

*\* Note: physical examinations may be performed by physicians, advanced practice nurses, physician assistants, or nurses.*

## 8.2 Laboratory Evaluations

### 8.2.1 Clinical Laboratory Evaluations

No clinical safety laboratory studies will be performed as part of this protocol.

To further describe the enrolled population, we will document the following from existing site medical records and laboratory results:

- White blood cell count and differential including site-specific normal ranges,
- Results of blood or respiratory tract cultures, antigen tests, or molecular assays, and
- *Streptococcal pneumoniae* or *Legionella pneumophila* serotype 1 urinary antigen testing.

### 8.2.2 Special Assays or Procedures

N/A

### 8.2.3 Specimen Preparation, Handling and Shipping

#### 8.2.3.1 Instructions for Specimen Preparation, Handling, and Storage

At the time of enrollment, a serum or plasma sample and nasopharyngeal sample will be collected. If the subject consented for future use, then PAXgene Blood RNA will also be collected. Another serum or plasma sample will be obtained at the Day 5 visit.

Nasopharyngeal specimens will be collected using flocked swabs. These swabs will be placed in universal transport medium. See the MOP for detailed instructions on processing and storage of these samples.

If the subject consented for future use, the PAXgene tubes should be inverted 8-10 times and stored upright at room temperature for a minimum of two hours prior to processing. Refer to the MOP for detailed instructions on processing and storage of these samples.

The sample collection, preparation, and testing must follow the VIDAS B.R.A.H.M.S Procalcitonin (PCT) package insert, also referred to as Instruction for Use (IFU). Additional details are described in the MOP. For this protocol it is preferred that a green-top lithium heparin tube is used for the collection of plasma but a red-top serum separator tube is also allowable.

**Note:** *Blood sampling tube results may vary from one manufacturer to another depending on the materials and additives use. It is the responsibility of each laboratory to validate the type of sample tube used and to follow the manufacturer's recommendations for use.*

*It is recommended not to use samples which appear to be hemolyzed, lipemic, or icteric and, if possible, to collect a new sample.*

*Samples collected in EDTA tubes cannot be used for PCT testing in this trial.*

Specific instructions are included in the Manual of Procedures (MOP).

#### **8.2.3.2 Specimen Shipment**

Nasopharyngeal swabs and serum/plasma samples will be shipped on dry ice to the DMID CMS in batches using only IATA-approved Category B shipping boxes. All packages will be labeled and documented correctly per current regulations, and a detailed manifest will be included. Packages will be shipped priority overnight, tracked en route, and delivery will be confirmed to ensure the package arrived in good condition. A specimen tracking log will be completed for every shipment.

Specific instructions will be included in the Manual of Procedures (MOP).

